4. STUDY DESIGN

4.1 OVERALL DESIGN

An overview of the study design is provided in Section 1.2.

Study BP41192 is a randomized, adaptive, placebo-controlled parallel group study to investigate the safety, tolerability, immunogenicity and pharmacokinetics of single ascending intravenous doses of RO7126209 in healthy participants.

This study uses a parallel group design, with participants recruited in 5 planned sequential cohorts. Participants will receive a single IV dose of either RO7126209 or placebo. Thirty-six participants are expected to be enrolled in this study. [REDACTED], with the maximum number of participants not exceeding 60. A minimum of 4 active treatment and 2 placebo participants will be included in the first two dose levels. Starting at dose level 3, and in all subsequent cohorts, a minimum of 6 active treatment and 2 placebo participants will be included. Based upon the review of emerging data there will be the option to adjust the number of participants on active treatment or placebo per dose level. If a dose level is repeated or if a lower dose is investigated, the added group will consist of at least 2 participants on active and 1 on placebo.

In accordance with standard practice for first-in-human studies, RO7126209 doses will be administered in ascending order, starting with a dose of 0.1 mg/kg that is anticipated to be well tolerated (Section 4.3.1). Subsequent doses will be selected in an adaptive manner during study conduct based on emerging safety, tolerability and PK data. A Bayesian adaptive design using the continual reassessment method (CRM) for predicting (see Section 9.3.4 and Appendix 6) the anticipated maximum dose-limiting event (DLE) rate to guide dose effect relationship will also be applied for dose escalation.

Intermediate dose escalation steps other than those anticipated (Section 1.2) may be used, doses may be repeated, or adjusted based on safety, tolerability and PK data at each dose level, as well as on model-based prediction of the anticipated maximum DLE rate.

In each dose group, sentinel dosing will be employed to allow for an evaluation of safety data by the Investigator up to 48 hours following intravenous administration of RO7126209 or placebo before subsequent participants are dosed. [REDACTED]

There will be at least 2 weeks between each dose level in order to permit adequate time for collation and review of emerging data before the next dose is administered.

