Grade 2	
 • Follow all Grade 1 recommendations. • Monitor cardiac and other organ function closely. • Hemodynamic support as indicated. • Oxygen for hypoxia. • Admit to ICU as appropriate. • If no improvement within 24 hours: 
 – Notify Medical Monitor. – Consider administering tocilizumab 8 mg/kg e IV as a single dose. • ADA and PK levels should be drawn.
Grade 3	
 • Notify Medical Monitor. • Cardiopulmonary and organ function monitoring in Intensive Care Unit. • Hemodynamic support as indicated. • Oxygen for hypoxia. • Other supportive care as clinically indicated (e.g., fever and neutropenia, infection). • Administer tocilizumab 8 mg/kg IV. 
 – If no clinical improvement within 24 hours: Administer repeat dose of tocilizumab 8 mg/kg. Consider initiating IV corticosteroids (e.g., methylprednisolone [2 mg/kg/day] or dexamethasone 10 mg for neurologic symptoms). • Labs: [REDACTED] within 3 hours of the event and to be repeated in 48 - 72 hours post event. ADA and PK levels should be drawn.
Grade 4	
 • Follow all Grade 3 management guidelines Labs: [REDACTED] within 3 hours of the event and to be repeated in 48 – 72 hours post event. ADA and PK levels should be drawn.

In case of signs/symptoms of IRR in the sentinel cohort, IRR risk mitigation steps may be implemented in the remaining participants of the dose level and the higher dose levels. The same approach will applied in case of signs/symptoms of IRRs in the

participants enrolled in the main cohort at a certain dose level for the higher dose levels. In order to reduce the occurrence and potential impact of IRRs, slower infusion time may be applied to all participants of the cohort (and the cohorts at higher dose level), after discussion and approval by the medical monitor.

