8.7 IMMUNOGENICITY ASSESSMENTS

As RO7126209 is a bispecific monoclonal antibody there is a risk that ADA against RO7126209 could develop, potentially reducing its efficacy and/or potentially resulting in symptomatic hypersensitivity reaction, including immune-complex reactions. Antibodies to RO7126209 will be evaluated in blood samples collected from all participants according to the SoA (Section 1.3). ADA data will not be required for dose escalation decisions.

[REDACTED]

[REDACTED]

[REDACTED]. The date and time of each sample will be recorded in the eCRF.

[REDACTED]

The blood samples will be destroyed 6 months after the release of final bioanalytical report at the CRO performing the analysis or shipped to Roche. In the latter case the samples may be stored up to 2 years after the date of final CSR. Details on sampling procedures, sample storage and shipment are given in the sample documentation.
Details on sampling procedures, sample storage and shipment are described in the sample documentation.

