9.3.5 Immunogenicity Analyses

The immunogenicity analyses will include all participants with at least one ADA assessment, irrespective of whether or not the participant receives any treatment ([Shankar et al 2014](#)).

The numbers and proportions of ADA-positive participants and ADA-negative participants at baseline (baseline prevalence) and after study drug administration (post-baseline incidence during both the treatment and follow-up periods) will be summarized.

- Participants are considered to be ADA positive if they are ADA negative at baseline but develop an ADA response following study drug administration (treatment-induced ADA response), or if they are ADA positive at baseline and the titer of one or more post-baseline samples is greater than the titer of the baseline sample by a scientifically reasonable margin such as at least 4-fold (treatment-enhanced ADA response).

- Participants are considered to be ADA negative if they are ADA negative at baseline and all post-baseline samples are negative, or if they are ADA positive at baseline but do not have any post-baseline samples with a titer that is greater than the titer of the baseline sample by a scientifically reasonable margin such as at least 4-fold (treatment unaffected).

The relationship between ADA status and safety, efficacy, PK, and biomarker endpoints will be analyzed and reported descriptively via subgroup analyses.

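### The ADA-safety and ADA-PK summaries reuse an incidence label that does not separate who had ADA at dosing, so contrasts for first-day reactions and early PK can be diluted or reversed

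*Combined protocol and SAP*

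**What the plan says.** Section 4.1 states: "Participants will receive a single IV dose of either RO7126209 or placebo". Table 1 schedules ADA samples on Day 1, Day 8 (168 h), Day 43 and Day 57, and Table 2 places the Day 1 sample before dosing.

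Section 9.3.5 classes as ADA positive those who are negative at baseline and respond after dosing (treatment-induced). It also includes those positive at baseline for whom the "titer of one or more post-baseline samples is greater than the titer of the baseline sample by a scientifically reasonable margin", with at least 4-fold as the example (treatment-enhanced). ADA negative are those negative throughout, and also those "ADA positive at baseline but do not have any post-baseline samples with a titer that is greater" by that margin (treatment-unaffected).

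The section reports counts "at baseline (baseline prevalence) and after study drug administration". It closes: "The relationship between ADA status and safety, efficacy, PK, and biomarker endpoints will be analyzed and reported descriptively via subgroup analyses". Table 9 carries nearly the same sentence. Neither place gives a second definition of status or a timing rule.

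Section 8.7 describes ADA as "potentially resulting in symptomatic hypersensitivity reaction, including immune-complex reactions". In section 8.3.7, Tables 7 and 8 add for infusion reactions of Grade 2 or higher, and Table 7 for anaphylaxis, that "ADA and PK levels should be drawn".

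**The concern.** The label is a sound way to report treatment-emergent incidence. The difficulty comes when it is used unchanged to relate ADA to outcomes that are over before the dose could have induced any ADA.

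Section 8.3.7 says that infusion reactions typically occur during the infusion or within 24 hours. Cend and AUC0-24h are complete by then too. For these outcomes the useful question is whether ADA was present at dosing. The plan's grouping does not ask it. Some participants with ADA at dosing sit in the negative group, and the positive group may consist largely of participants who had none at dosing.

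Immunogenicity is a secondary objective, and this is the only ADA-safety analysis visible in the document. A descriptive table with mismatched groups can still lead its reader to the wrong conclusion about pre-existing ADA.

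**Working it through.** **1. Group size.** Section 9.1 gives minimum cohorts of 4 active + 2 placebo at dose levels 1 and 2, and 6 + 2 from level 3. With five cohorts, active = 2×4 + 3×6 = 26 and placebo = 5×2 = 10. The total of 36 reproduces the planned enrolment.

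**2. Timing.** The first scheduled post-dose ADA sample is at 168 h. Reactions within 24 hours, Cend and AUC0-24h are complete about 168 - 24 = 144 h earlier. AUC0-168h ends when that sample is drawn. CL, half-life and AUC0-inf draw on PK samples scheduled to Day 57.

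**3. How many participants could be affected.** The document gives no baseline ADA prevalence, so a range is assumed. Expected number among 26 active = 26p, and the chance of at least one = 1 - (1 - p)^26.

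| Assumed prevalence p | Expected with pre-existing ADA | Chance of at least one |
|---|---|---|
| 2% | 0.5 | 0.41 |
| 5% | 1.3 | 0.74 |
| 10% | 2.6 | 0.94 |
| 20% | 5.2 | 0.997 |

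**4. Effect of the grouping on a first-day contrast.** Let b be the share of baseline-positive participants whose titre is boosted, and t the share of baseline-negative participants with treatment-induced ADA. Assume a first-day reaction rate of r1 = 50% with ADA at dosing and r0 = 10% without. None of these values is in the document. Grouping by predose status gives 50 - 10 = +40 points. Under section 9.3.5:

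- rate in ADA positive = [p·b·r1 + (1-p)·t·r0] / [p·b + (1-p)·t]
- rate in ADA negative = [p·(1-b)·r1 + (1-p)·(1-t)·r0] / [p·(1-b) + (1-p)·(1-t)]

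For p = 10%, t = 30%, b = 0:

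- positive = 0.027/0.27 = 10.0%
- negative = (0.050 + 0.063)/(0.10 + 0.63) = 0.113/0.73 = 15.5%
- contrast = -5.5 points

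With p and t held at these values:

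| Boosted share b | ADA positive | ADA negative | Contrast (points) |
|---|---|---|---|
| 0 | 10.0% | 15.5% | -5.5 |
| 25% | 13.4% | 14.3% | -0.9 |
| 50% | 16.3% | 12.9% | +3.3 |
| 100% | 20.8% | 10.0% | +10.8 |

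Over p of 5% to 20%, b of 0 to 100% and t of 10% to 50%, the extremes are:

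- p = 20%, b = 0, t = 50%: 10.0% against 0.14/0.60 = 23.3%, a contrast of -13.3 points
- p = 20%, b = 100%, t = 10%: 0.108/0.28 = 38.6% against 10.0%, a contrast of +28.6 points

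The contrast is zero when b = t, because both groups then contain the same share of baseline-positive participants. It reverses when t exceeds b. In every case tried it is smaller in size than the true 40 points.

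**The case against.** The strongest reply is that the section does not claim to explain first-day reactions. Section 8.7 speaks of ADA that could develop, and names immune-complex reactions without tying them to Day 1. Section 8.3.7 says IgE-mediated hypersensitivity generally does not occur at first exposure. First-day reactions also have a separate planned analysis, of predose and 6-hour samples against dose and cytokine release. Prior gantenerumab and hypersensitivity to biologics are exclusions. Baseline prevalence is already tabulated, ADA data are not needed for dose escalation, and parts of section 8.7 are redacted.

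Much of this stands, and it limits the point to a descriptive analysis. It does not remove it. The relationship sentence covers safety and PK without a time limit, the cytokine analysis does not address ADA, and the protocol's own categories foresee participants with ADA before dosing. ADA status could be read to include baseline status, but the plan does not say so.

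A reader might infer four stronger things that the document does not support:

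- **All pre-existing ADA is counted as negative.** Treatment-enhanced participants are classed as positive.
- **The analysis cannot detect ADA-related reactions.** Later events and late PK can still be related to post-baseline ADA, and part of a first-day signal survives when many baseline-positive participants are boosted.
- **AUC0-168h is compared backwards in time.** ADA found on Day 8 may have arisen during that interval.
- **Event-driven samples push reactors into the positive group.** A response induced within 24 hours is unlikely, and baseline-positive participants would still need the titre margin.

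**Conclusion.** The point holds for infusion reactions within 24 hours, Cend and AUC0-24h. For these, section 9.3.5 groups participants by a status that partly reflects ADA arising after the outcome, and it mixes participants who had ADA at dosing with those who never had it. This can weaken or reverse the descriptive contrast: under the assumed rates, from a true +40 points to between -13.3 and +28.6.

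That range rests wholly on assumed prevalence, boosting, induction and reaction rates. If pre-existing ADA is rare (2% assumed), the chance that any active participant is affected is only 0.41. The conclusion also assumes that the redacted parts of section 8.7 give no separate rule. The data needed are already planned, so the gap lies in the analysis specification. This is a worthwhile, cheap improvement and not a threat to the study's main conclusions.

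**What to change.** Keep the present definitions for ADA incidence. For the relationship analyses in section 9.3.5 and Table 9:

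- Summarise reactions within 24 hours, Cend and AUC0-24h by predose ADA status.
- For later adverse events, AUC0-168h, CL, half-life and AUC0-inf, show four groups separately: never positive, treatment-unaffected, treatment-enhanced and treatment-induced.
- Do not drop adverse events that precede the first positive sample. Scheduled sampling jumps from Day 8 to Day 43, so an event on Day 20 may belong to a response first seen on Day 43. Give a participant listing with event onset set against the last negative and first positive samples.
- Keep event-driven ADA samples, since they are closest to the reaction, and flag them in the listing.

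This changes text and table shells only and needs no new samples. The cost is small cells, with about 26 active participants spread over up to four groups, so the listing will carry most of the information.

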9.3.6 Pharmacokinetic / Safety Relationships

Exploratory investigation of the relationship between plasma exposure of RO7126209 and safety measurements may be performed.

9.4 SUMMARIES OF CONDUCT OF STUDY

All protocol deviations will be listed. Data for study drug administration and concomitant medication will be listed. The number of participants who were randomized, discontinued, and completed the study will be summarized and listed.

1. REGULATORY AND ETHICAL CONSIDERATIONS

1.1. COMPLIANCE WITH LAWS AND REGULATIONS

This study will be conducted in full conformance with the ICH E6 guideline for Good Clinical Practice and the principles of the Declaration of Helsinki, or the laws and regulations of the country in which the research is conducted, whichever affords the greater protection to the individual. The study will comply with the requirements of the ICH E2A guideline (Clinical Safety Data Management: Definitions and Standards for Expedited Reporting). Studies conducted in the United States or under a U.S. Investigational New Drug (IND) application will comply with U.S. FDA regulations and applicable local, state, and federal laws. Studies conducted in the EU/EEA will comply with the EU Clinical Trial Directive (2001/20/EC).

1.2. INSTITUTIONAL REVIEW BOARD OR ETHICS COMMITTEE

This protocol, the ICFs, any information to be given to the participant (e.g., advertisements, diaries etc), and relevant supporting information must be submitted to the IRB/EC by the Principal Investigator and reviewed and approved by the IRB/EC before the study is initiated. In addition, any participant recruitment materials must be approved by the IRB/EC.

The Principal Investigator is responsible for providing written summaries of the status of the study to the IRB/EC annually or more frequently in accordance with the requirements, policies, and procedures established by the IRB/EC. Investigators are also responsible for promptly informing the IRB/EC of any protocol amendments (Section 2.3.1 of this Appendix).

The Investigator should follow the requirements for reporting all adverse events to the Sponsor. Investigators may receive written IND safety reports or other safety-related communications from the Sponsor. Investigators are responsible for ensuring that such reports are reviewed and processed in accordance with Health Authority requirements and the policies and procedures established by their IRB/EC, and archived in the site's study file.

1.3. INFORMED CONSENT

The Sponsor's Master Informed Consent Form (and ancillary sample ICFs such as a Child's Assent or Caregiver's Informed Consent Form, if applicable) will be provided to each site. If applicable, it will be provided in a certified translation of the local language. Participants must be informed that their participation is voluntary. Participants or their legally authorized representative will be required to sign a statement of informed consent that meets the requirements of 21 CFR 50, local regulations, ICH guidelines, Health Insurance Portability and Accountability Act (HIPAA) requirements, where applicable,

and the IRB/IEC or study center. The Sponsor or its designee must review and approve any proposed deviations from the Sponsor's sample ICFs or any alternate consent forms proposed by the site (collectively, the "Consent Forms") before IRB/EC submission. The final IRB/EC-approved Consent Forms must be provided to the Sponsor for Health Authority submission purposes according to local requirements. Participants must be re-consented to the most current version of the ICF(s) during their participation in the study. A copy of the ICF(s) signed by all parties must be provided to the participant or the participant's legally authorized representative.

The Consent Forms must be signed and dated by the participant or the participant's legally authorized representative before his or her participation in the study. The case history or clinical records for each participant shall document the informed consent process and that written informed consent was obtained prior to participation in the study.

The Consent Forms should be revised whenever there are changes to study procedures or when new information becomes available that may affect the willingness of the participant to take part. The final revised IRB/EC-approved Consent Forms must be provided to the Sponsor for Health Authority submission purposes if required as per local regulations.

Participants must be re-consented to the most current version of the Consent Forms (or to a significant new information/findings addendum in accordance with applicable laws and IRB/EC policy) during their participation in the study. For any updated or revised Consent Forms, the case history or clinical records for each participant shall document the informed consent process and that written informed consent was obtained using the updated/revised Consent Forms for continued participation in the study.

A copy of each signed Consent Form must be provided to the participant or the participant's legally authorized representative. All signed and dated Consent Forms must remain in each participant's study file or in the site file and must be available for verification by study monitors at any time.

Each Consent Form may also include participant authorization to allow use and disclosure of personal health information in compliance with the U.S. Health Insurance Portability and Accountability Act of 1996 (HIPAA). If the site utilizes a separate Authorization Form for participant authorization for use and disclosure of personal health information under the HIPAA regulations, the review, approval, and other processes outlined above apply except that IRB review and approval may not be required per study site policies.

1.4. CONFIDENTIALITY

Participants will be assigned a unique identifier by the Sponsor. Any participant records or datasets that are transferred to the Sponsor will contain the identifier only; participant

names or any information which would make the participant identifiable will not be transferred.

The participant must be informed that his/her personal study-related data will be used by the Sponsor in accordance with local data protection law. The level of disclosure must also be explained to the participant.

Medical information may be given to a participant's personal physician or other appropriate medical personnel responsible for the participant's welfare, for treatment purposes.

The participant must be informed that his/her medical records may be examined by Clinical Quality Assurance auditors or other authorized personnel appointed by the sponsor, by appropriate IRB/IEC members, and by inspectors from regulatory authorities.

Study data may be submitted to government or other health research databases or shared with researchers, government agencies, companies, or other groups that are not participating in this study. These data may be combined with or linked to other data and used for research purposes, to advance science and public health, or for analysis, development, and commercialization of products to treat and diagnose disease. In addition, redacted clinical study reports and other summary reports will be provided upon request.

1.5. FINANCIAL DISCLOSURE

Investigators will provide the Sponsor with sufficient, accurate financial information in accordance with local regulations to allow the Sponsor to submit complete and accurate financial certification or disclosure statements to the appropriate Health Authorities. Investigators are responsible for providing information on financial interests during the course of the study and for one year after completion of the study (i.e., LPLV)

2. DATA HANDLING AND RECORD

2.1. DATA COLLECTION AND MANAGEMENT RESPONSIBILITIES

2.1.1. Data Quality Assurance

All participant data relating to the study will be recorded on printed or electronic CRF unless transmitted to the Sponsor or designee electronically (e.g., laboratory data). The Investigator is responsible for verifying that data entries are accurate and correct by physically or electronically signing the CRF.

The Investigator must maintain accurate documentation (source data) that supports the information entered in the CRF.

The Investigator must permit study-related monitoring, audits, IRB/IEC review, and regulatory agency inspections and provide direct access to source data documents.

The Sponsor or designee is responsible for the data management of this study including quality checking of the data.

Study monitors will perform ongoing source data verification to confirm that data entered into the CRF by authorized site personnel are accurate, complete, and verifiable from source documents; that the safety and rights of participants are being protected; and that the study is being conducted in accordance with the currently approved protocol and any other study agreements, ICH GCP, and all applicable regulatory requirements.

